Perform physical examination		✓							✓	
Urine pregnancy test	✓	✓	✓	✓	✓	✓	✓	✓	✓	✓

	Screening		BL	Treatment Period						Follow Up
	Visit 1	Visit 1a	Visit 2	Visit 3	Visit 4	Visit 5	Visit 6	Visit 7	Visit 8	Visit 9 or 4-Week Post Early Termination Visit
Activity	Week -12 to Week -4	Day -28/ Week -4	Day 1/ Week 0	Day 29/ Week 4	Day 57/ Week 8	Day 85/ Week 12	Day 113/ Week 16	Day 141/ Week 20	Day 169/ Week 24	Day 197/ Week 28
Visit Windows	N/A	Day -35 to Day -28	N/A	± 3 days	± 3 days	± 3 days	± 3 days	± 3 days	± 3 days	± 3 days
 CENTRAL LABS										
Collect clinical laboratory samples		✓	✓	✓	✓	✓	✓	✓	✓	
Lipid profile, marker of inflammation, adipokine hormones, HbA1c			✓						✓	
Optional blood samples for genomics			✓							
Optional biomarker collection for CGRP (saliva and plasma)			✓			✓			✓	
Urine drug and alcohol screen		✓								
 TREATMENT										
Atogepant dosing (daily until Visit 8)			✓							
Dispense study drug			✓	✓	✓	✓	✓	✓		
Administer BOTOX injection (concomitant medication), ± 7 days from Visits 2, 5 and 8 dates			✓ (±7 days)			✓ (±7 days)			✓ (±7 days)	

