3.13 Clinical Laboratory Tests

The blood samples for serum chemistry tests will be collected prior to study drug intake (except for the Screening Visit). An 8-hour fast is preferred but not required prior to blood sample collection. The baseline laboratory test results for clinical assessment for a particular test will be defined as the last measurement prior to the initial dose of study drug.

A certified laboratory will be utilized to process and provide results for the clinical laboratory tests. Laboratory reference ranges will be obtained prior to the initiation of the study.

Instructions regarding the collection, processing, and shipping of these samples will be provided by the central laboratory.

If a laboratory test value is outside the reference range and the investigator considers the laboratory result to be clinically significant, the investigator will:

- repeat the test to verify the out-of-range value;
- follow the out-of-range value to a satisfactory clinical resolution; or

- discontinue the participant from the study or require the participant to receive treatment; in this case, the laboratory result will be recorded as an AE.

Clinical Laboratory Tests		
Hematology	Clinical Chemistry ^a	Urinalysis
Hematocrit Hemoglobin Red blood cell (RBC) count Red blood cell indices (mean corpuscular volume, mean corpuscular hemoglobin, mean corpuscular hemoglobin concentration) White blood cell (WBC) count Neutrophils Bands Lymphocytes Monocytes Basophils Eosinophils Platelet count (estimate not acceptable)	Blood urea nitrogen (BUN) Creatinine Creatine kinase Total bilirubin Direct and indirect bilirubin Gamma-glutamyl transferase (GGT) Lactate dehydrogenase (LDH) Alanine aminotransferase (SGPT/ALT) Aspartate aminotransferase (SGOT/AST) Alkaline phosphatase Sodium Potassium Calcium Inorganic phosphorus Total protein Glucose Albumin Chloride Bicarbonate/CO ₂ Uric acid Cholesterol Triglycerides Estimated glomerular filtration rate (GFR) Calculation	Specific gravity Ketones pH Protein Blood Microscopic examination including red blood cells/high-power field, white blood cells/high-power field, and casts/low-power field ^b Glucose
		Other Tests

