		Urine human chorionic gonadotropin ^c Follicle-stimulating hormone ^d Marker of Inflammation: TNF α – Serum ^e Marker of Inflammation: C- Reactive Protein (CRP) ^e Adipokine Hormones: Adiponectin - serum or plasma ^e Adipokine Hormones: leptin - serum or plasma ^e Hormones: GLP-1 ^e Glucose metabolism: HbA1c - separate collection ^e Lipid profile: LDL ^e Lipid profile: HDL ^e Lipid profile: VLDL ^e Lipid profile: NEFAs (FFAs) ^e Urine drug screen: alcohol, opiates, barbiturates, amphetamines, cocaine, benzodiazepines, alcohol, phencyclidine, methadone
Coagulation		
Prothrombin time (PT)/INR		
Serology^b		
Hepatitis B surface antigen ^b Anti-hepatitis C antibody ^b		

FFA = free fatty acids; GLP-1 = glucagon-like peptide 1; HbA1c = hemoglobin A1c; HDL = high-density lipoprotein; INR = international normalized ratio; LDL = low-density lipoprotein; NEFA = non-esterified fatty acids; TNF α = TNF alpha; VLDL = very low-density lipoprotein

- All chemistries should be performed at all visits.
- Performed only at screening.
- Pregnancy testing is not required for females of nonchildbearing potential. Test materials are provided by central lab, but testing is performed locally.
- Performed only at screening for females aged ≤ 55 years with no menses for 12 months without an alternative medical cause for menopause.
- Performed only at Visit 2 and Visit 8.

Clinical Laboratory Kits for Incidences of Elevated ALT or AST		
ALT/AST Confirmation	ALT/AST Investigation	ALT/AST Follow-up

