10.3 Analysis of Laboratory Data

Data collected from central laboratories, including additional laboratory testing due to an SAE, will be used in all analyses, except for Baseline where SAE-related laboratory assessments on or before the first dose of study drug will be excluded. The clinical laboratory tests defined in the protocol operations manual (e.g., hematology, clinical chemistry, and urinalysis) will be summarized.

Each laboratory variable will be summarized for all time points (starting with Baseline) with the number of non-missing observations, mean and standard deviation, median, Q1, Q3, minimum and maximum. Mean change from baseline to each applicable post-baseline visit will be summarized, with the number of observations, baseline mean, and visit mean. The change from baseline mean will be presented for the mean change from baseline. In addition, descriptive statistics for values and changes from the baseline values in conventional units at each assessment time point will be presented for selected clinical laboratory parameters listed in [Appendix E](#). A description of reporting the lab values in conventional units in patient narratives (along with the standard reporting in SI units) is presented at the end of [Appendix E](#).

Changes in laboratory parameters will be tabulated using shift tables categorized as low, normal, or high based on the normal ranges of the laboratory used for each sample. A shift table will be provided to summarize shifts from baseline to the final post-baseline value.

Laboratory abnormalities will be evaluated based on Potentially Clinically Significant (PCS) criteria (Appendix Table D-1). For each laboratory PCS criterion, the number and percentage of participants who have a laboratory value meeting the criteria will be summarized. Listings will be provided to summarize participant-level laboratory data for participants meeting PCS criteria.

In addition, ALT, AST, alkaline phosphatase, and total bilirubin will be categorized in Table D-2. The number and percentage of participants meeting each of the criteria for postbaseline hepatic laboratory abnormalities listed in Table D-2 will be summarized. The percentages will be calculated relative to the number of participants with at least 1 available postbaseline assessment. The numerator will be the total number of participants having at least 1 postbaseline value that meets the specific category during the study. A supportive listing will also be provided.

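### The laboratory shift table uses only the final post-baseline value, so resolved abnormalities in about ten panel tests, and resolved sub-threshold values in others, enter no planned laboratory count

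*SAP*

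**What the plan says.** SAP 10.3 describes the shift analysis in two sentences. The first sets the categories: "Changes in laboratory parameters will be tabulated using shift tables categorized as low, normal, or high". The second sets the time point: "A shift table will be provided to summarize shifts from baseline to the final post-baseline value". No shift to a worst value, and no shift by visit, is specified.

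The sampling is much denser than that. In Protocol Appendix D the row "Collect clinical laboratory samples" is ticked at Visits 1a and 2 and at each of Visits 3 to 8. Operations Manual 3.13 adds, for chemistry, "All chemistries should be performed at all visits".

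SAP 10.3 also plans three other outputs that are not tied to the final visit:

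- PCS counts against Table D-1: "For each laboratory PCS criterion, the number and percentage of participants who have a laboratory value meeting the criteria will be summarized". Participant-level listings accompany them.
- Hepatic categories against Table D-2, which covers ALT, AST, alkaline phosphatase and total bilirubin: "The numerator will be the total number of participants having at least 1 postbaseline value that meets the specific category during the study".
- Descriptive statistics by visit: "Each laboratory variable will be summarized for all time points (starting with Baseline) with the number of non-missing observations", followed by the mean, SD, median, quartiles, minimum and maximum.

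**The concern.** Safety is the primary objective (SAP 3.1), and an on-treatment laboratory change that settles with continued dosing is one form a drug effect can take. A table built on the last value shows only what persists to, or first appears at, the last draw. That would not matter if every test had another count covering all visits, but not every test does. For tests without a PCS or hepatic criterion, and for values between the normal limit and the PCS limit, the final-value shift is the only planned laboratory table that counts participants as abnormal. An abnormality that resolved by the last draw would not be counted in it.

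**Working it through.** **The plan's own safety figure.** SAP 2.4 states a 95% probability of seeing at least one event of 4% incidence in 75 participants. 1 − 0.96^75 = 0.953, so the figure reproduces. The expected number of cases is 75 × 0.04 = 3. The shift-table text itself states no figure.

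**Draws available and used.** Scheduled post-baseline draws are Visits 3, 4, 5, 6, 7 and 8, so six. The shift table uses one. For a completer, 6 − 1 = 5 are unused; early discontinuers have fewer.

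**Tests without another count.** I compared the panel in Operations Manual 3.13 with SAP Tables D-1 and D-2.

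| Group | Panel items | Table D-1 rows | No row in D-1 or D-2 |
|---|---|---|---|
| Chemistry | 24 | 21 | GGT, direct bilirubin, indirect bilirubin |
| Hematology | 14 | 10 | MCV, MCH, MCHC, bands |
| Urinalysis | 7 | 4 | ketones, blood, microscopy |
| Coagulation | 1 | 0 | PT/INR |
| Total | 46 | 35 | 11 |

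The footnote on urine microscopy reads as screening only. Setting it aside leaves 11 − 1 = 10 tests. Lipid fractions, inflammation markers, adipokines, GLP-1 and HbA1c are drawn only at Visits 2 and 8, so the final value is their only scheduled post-baseline value and they are unaffected.

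**Values with a row but short of it.** Table D-1 counts creatinine only above 1.5 × ULN, and creatine kinase and triglycerides only above 2 × ULN. A creatinine between 1 and 1.5 × ULN at Week 8 that is normal at Week 24 enters neither the PCS count nor the shift table as abnormal. The same holds for a change in a direction for which Table D-1 sets no limit. The four Table D-2 tests do not have this gap on the high side, because their categories start at 1 × ULN.

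**How often the final-value table misses such a value.** The timing is my assumption; the documents give none.

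- Present at one visit, equally likely at any of six: missed with probability 5/6 = 83%.
- Present at two consecutive visits: five possible pairs, one of which includes Visit 8, so 4/5 = 80% are missed.
- Present at two or three of the six, every visit equally likely to be affected: 4/6 = 67% or 3/6 = 50% are missed.

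At an assumed 4% incidence, the chance that the table shows at least one case is 1 − (1 − 0.04 × k/6)^75 for an abnormality present at k visits. This gives 39%, 63% and 78% for k = 1, 2 and 3. A worst-value shift gives 95%.

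**Chance crossings with a worst-value table.** If a normal range leaves 2.5% in each tail and draws were independent, the extreme of six crosses one limit with probability 1 − 0.975^6 = 14.1%. In 75 participants that is 75 × 0.141 = 10.6, against 75 × 0.025 = 1.9 for a single draw. Repeated draws in one person are usually positively correlated, so 14.1% is best read as an upper figure.

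**The case against.** The strongest reply is that the shift table is one of several laboratory outputs and that the others cover what matters most. Much of this stands.

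- Both adverse events of special interest are hepatic, and Table D-2 counts their components at any post-baseline visit.
- The PCS counts and listings have no final-visit limit and cover 35 of the 46 panel items.
- A single extreme value in any numeric test would show in that visit's minimum or maximum.
- Under Protocol 6.1 a laboratory abnormality becomes an adverse event if it leads to discontinuation, needs treatment, meets protocol criteria or is judged one by the investigator. It then enters the adverse event tables whether or not it resolves. The data monitoring committee also reviews laboratory values.
- Several uncounted tests sit next to counted ones: bilirubin fractions beside total bilirubin, red cell indices beside hemoglobin, bands beside neutrophils.
- The every-visit footnote covers chemistry only. Six draws for hematology, urinalysis and PT/INR rest on the general sampling row in Appendix D, and coagulation is not named among the laboratory safety endpoints.
- A worst-value table in a single-arm study collects chance crossings with no comparator to set them against.

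These points narrow the gap without closing it. A minimum or maximum does not count participants or relate them to baseline status, and it says little for dipstick results such as ketones and blood. The adverse event route depends on the listed conditions or the investigator's judgement. The chance-crossing point limits how an added table may be read, but it does not make the final value alone an adequate summary.

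A reader might infer that a resolved laboratory abnormality appears nowhere in the planned output, or that a transient liver signal could be lost. The documents do not support either reading, for the reasons in the first four items.

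**Conclusion.** The point holds as a limited reporting gap in the primary, safety domain. It covers ten tests with no Table D-1 or D-2 criterion and, for tests outside Table D-2, out-of-range values that stay short of the PCS limit and resolve before the last draw.

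The 83% figure rests on assumed one-visit duration and uniform timing over six visits, and 50% to 80% applies under the longer durations shown. It would be tempting to quote it as the share of laboratory abnormalities the study will miss. It is only the miss rate of one table for this restricted set of values, and it does not apply to hepatic tests or PCS-level results. Five unused draws is the count for completers; the plan itself allows for 20% early termination.

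No stated figure, sample size or error rate changes, and the documents do not contradict themselves here. The change is worth making because it is cheap and serves the primary objective.

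**What to change.** In SAP 10.3, add low/normal/high shifts from baseline to the lowest and to the highest post-baseline value, using all scheduled and unscheduled central laboratory values. For dipstick items such as ketones and blood, the most abnormal category is enough. Keep the final-value shift, which shows what persists.

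Label the added tables as a screen and state that they are to be read with the PCS, hepatic and adverse event tables. Add a sentence saying that the extreme of several draws crosses a normal limit by chance more often than one draw does (up to about 14% against 2.5% per tail under independence), and that there is no control arm.

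The cost is one further set of shift tables and a few lines of SAP text. No new samples or visits are needed, and SAP 10.3 already brings additional central laboratory draws made because of a serious adverse event into the analyses.

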10.4 Analysis of Vital Signs

Vital sign measurements of systolic and diastolic blood pressure, pulse rate, respiratory rate, body weight, and body temperature will be summarized.

Each vital sign variable will be summarized for all time points (starting with Baseline) with the number of non-missing observations, mean and standard deviation, median, Q1, Q3, minimum and maximum. Mean change from baseline to each applicable post-baseline visit will be summarized for each vital sign variable, with the number of observations, baseline mean, and visit mean. The change from baseline mean and standard error will be presented for the mean change from baseline.

Vital sign variables will be evaluated based on PCS criteria (Table D-3). For each vital sign PCS criterion, the number and percentage of participants who have a vital sign value meeting the criteria will be summarized. Listings will be provided to summarize participant-level vital sign data for participants meeting PCS criteria.

10.5 Other Safety Analyses

10.5.1 Electrocardiogram

Descriptive statistics for ECG parameters (i.e., heart rate, PR interval, QRS interval, RR interval, QT interval, and QTc interval) at baseline, postbaseline, and changes from baseline values at each postbaseline timepoint will be presented.

ECG parameter values are considered PCS if ECG values meet either the actual value or change from baseline PCS high criteria listed in Table D-4. The number and percentage of

participants with PCS postbaseline values and postbaseline values of clinical interest listed in Table D-5 will be tabulated. The number and percentage of participants with PCS postbaseline values will be summarized. The percentages will be calculated relative to the number of participants with an available non-PCS baseline value and at least 1 postbaseline assessment. The numerator will be the total number of participants with an available non-PCS baseline value and at least 1 PCS postbaseline ECG value during the study. A supportive listing of participants with PCS postbaseline values will be provided. A listing of all AEs for participants with PCS ECG values will also be provided.

A shift table from baseline to the end of open-label treatment period in the overall interpretation of the ECG will be presented for the following categories: normal and abnormal. A tabular display of participants with postbaseline clinically significant ECG abnormalities according to the investigator's overall interpretation will be provided.

10.5.2 Columbia-Suicide Severity Rating Scale

For C-SSRS, the number and percentage of participants with suicidal ideation or suicidal behavior as recorded on the C-SSRS will be summarized for the Safety Population. The distribution of responses for most severe suicidal ideation and most severe suicidal behavior in the participant's lifetime history, in the past 6 months, in the open-label treatment period, and in the follow-up period will also be presented. Supportive listings will be provided and will include the subject number, study center number, lifetime history, and postbaseline values. Intensity of suicidal ideation and suicidal behavior type will also be included in these listings.

11.0 Interim Analyses

No interim analysis of efficacy data will be performed.

12.0 Data Monitoring Committee

An independent DMC has been established to review unblinded safety data and summary reports, identify any safety issues and trends, and make recommendations to AbbVie,

including ongoing trial conduct or modifications to the trial, if emerging data show unexpected and clinically significant AEs of treatment.

Details of the DMC memberships, standard operational procedures for data monitoring/review, frequency of review, and other pertinent details have been provided in a separate DMC Charter.

13.0 Overall Type-I Error Control

No multiplicity adjustment for overall Type I error control is planned for this study.

14.0 COVID-19 Related Analyses

14.1 Efficacy Evaluation

For the endpoints are collected via eDiary, minimal disruption is expected for these endpoints because participants are expected to complete eDiary at home and submit the responses every day.

The health outcome measures will be collected using eTablet as electronic patient reported outcomes (ePRO) at site. To evaluate the missing rate for these efficacy endpoints, the number of participants who missed at least one visit due to COVID-19 will be summarized at each visit in the efficacy analysis population.

14.2 Safety and Other Evaluations

This section specifies analyses related to COVID-19 pandemic from the following aspects:

- Disposition
- Study visits and study procedures
- Treatment discontinuation related to COVID-19
- TEAEs related to COVID-19 infection
- COVID-19 status (COVID-19 testing results or contact with a COVID-19 positive person)

- COVID-19 vaccination

The safety population will be used for the planned COVID-19 related analyses.

The number of participants impacted by COVID-19 during the study will be summarized. The number of participants who missed at least one entire visit, had impacted in-person clinic visits, and had virtual visits due to COVID-19 will be summarized.

The number of participants with TEAEs related to COVID-19 infection will be provided. COVID-19 status, i.e., testing results or contact with a COVID-19 positive person, will be summarized.

The number and percentage of participants who received a COVID-19 vaccine will be tabulated by Anatomical Therapeutic Chemical (ATC) 4 class and preferred term (PT). The number and percentage of participants with TEAEs related to COVID-19 vaccine will be summarized.

Supporting listings for the described analyses above will be provided.

15.0 Version History

Table 1. SAP Version History Summary

Version	Date	Summary
1.0	14 Apr 2023	Initial version
2.0	08 May 2025	
To align with Protocol v6.0:
 
 Updated simple size and allowed BOTOX dose (Section 2.2, Section 2.3, Section 2.4). 
To clarify efficacy analyses:
 
 Updated exploratory efficacy endpoints (Section 3.2) Clarified the baseline for efficacy (Section 9.1). Updated the analysis methods correspond to the changes in efficacy endpoints (Section 9.3.2) Updated derivation method for eDiary data based endpoints (Appendix B). 
To align with the actual data collection:
 
 Updated the section for subject disposition (Section 5.0). Updated the BOTOX related treatment duration and compliance (Section 6.0) Updated the section for participant characteristics (Section 7.1 and Section 7.2). Reorganized the language for TEAEs (Section 10.2.1, Section 10.2.3 and Section 10.2.4). Clarified the lab data will be included for analysis (Section 10.3). Updated the scope of being presented in lab, vital signs, and ECG. (Section 10.3, Section 10.4 and Section 10.5.1) Removed the summary analysis for the missed assessment due to COVID-19 by assessment category (Section 14.2) Updated PCS for estimated glomerular filtration rate and ECG parameters (Appendix D). 
To align with the clinical updates:
 
 Updated PCS for temperature, glucose and protein in urinalysis (Appendix D).

15.1 Changes to Planned Analyses in the Protocol

There are no changes to planned analyses described in protocol.

Appendix B. Derivation of Efficacy Endpoints Based on eDiary Data

Efficacy measures were defined as follow:

A migraine day is defined as any calendar day on which a headache occurs which meets Criteria A, B, and C OR meets Criteria D and E, as listed below, as per participant eDiary. Calendar days begin at midnight and last until 11:59 PM (23:59).

A. Headache has at least 2 of the following 4 characteristics:

- Unilateral location
- Pulsating quality
- Moderate or severe pain intensity
- Aggravated by or causing avoidance of routine physical activity (e.g., walking or climbing stairs)

B. At least one of the following:

- Nausea and/or vomiting
- Photophobia and phonophobia
- Typical aura (i.e., visual, sensory, or speech/language) accompanying or within 60 minutes before headache begins

C. Duration of headache lasting 2 hours or longer on a calendar day unless an acute, migraine-specific medication (i.e., triptan or ergot derivative) was used after the start of the headache, in which case no minimum duration will be specified.

OR

D. Any headache which fulfills 1 criterion from (1) and at least 1 criterion from (2)
OR fulfills at least 2 criteria from (1) and no criteria from (2).

1. Headache characteristics:

- Unilateral location
- Pulsating quality
- Moderate or severe pain intensity

- Aggravated by or causing avoidance of routine physical activity (e.g., walking or climbing stairs)
2. Symptoms:
 - Nausea and/or vomiting
 - Photophobia and phonophobia
 - Typical aura (i.e., visual, sensory, or speech/language) accompanying or within 60 minutes before headache begins
 1. Duration of headache lasting 2 hours or longer on a calendar day unless an acute, migraine specific medication (i.e., triptan, ergot derivative, or ditan) was used after the start of the headache, in which case no minimum duration will be specified.

A headache day is defined as any calendar day on which headache pain lasting 2 hours or longer occurs unless an acute headache medication (e.g., ibuprofen, triptan) was used after the start of the headache, in which case no minimum duration will be specified. Note that antiemetics will not be counted as an acute headache medication for headache day identification. Calendar days begin at midnight and last until 11:59 PM (23:59).

An acute medication use day is defined as any day on which a participant reports, per eDiary, the intake of allowed medication(s) to treat an acute migraine. The allowed medications include the following categories of drugs: triptans, ergots, opioids, analgesics (including acetaminophen), NSAIDs (including aspirin), and antiemetics.

A moderate or severe headache day is defined as a headache day during which the maximum pain intensity is either moderate or severe. Headache day pain intensity is defined as the worst pain intensity on any headache day where headache pain intensity will be subjectively rated by the patient on a scale from mild to severe:

- Mild pain (1)
- Moderate pain (2)
- Severe pain (3)

Moderate/severe headache day is defined as a headache day during which the maximum pain severity is either moderate or severe. Severe headache day is defined as a headache day during which the maximum pain severity is severe.

If participants experience no headache in a day, then the corresponding pain intensity of that day will be set as missing.

A headache free day is defined as any calendar day on which does not meet the definition of a headache day.

A complete migraine symptom-free day is defined as any calendar day on which a participant reports, per eDiary, no headache and no experience of any of the following non-headache symptom(s): Nausea and/or Vomiting, Sensitivity to light, Sensitivity to sound, Dizziness, Neck pain, Tiredness, Mood change, Yawning, Thirst, Cravings, Urinary frequency, and other (Forehead/facial sweating, Abnormal shedding of tears, Nasal congestion, Eyelid swelling, and Runny nose).

A cardinal migraine symptom-free day is defined as any calendar day on which a participant reports, per eDiary, no headache and no experience of any of the following non-headache symptom(s): Nausea and/or Vomiting, Sensitivity to light, and Sensitivity to sound.

A day with an individual non-headache symptom for each of the 5 most common and cardinal individual non-headache symptoms is defined as any calendar day on which a participant reports, per eDiary, the each of the 5 most common individual non-headache symptoms. 5 most common individual non-headache symptoms are defined as the 5 most common individual non-headache symptoms reported by participants, per eDiary, during the baseline period. The monthly days with individual non-headache symptoms days (including difficulty with concentration and/or thinking clearly, see definition in SPP Section 4.2) during the baseline period will be summarized and sorted by decreasing mean. Other (Forehead/facial sweating, Abnormal shedding of tears, Nasal congestion, Eyelid swelling, and Runny nose) will be renamed as cranial autonomic symptoms. If the

cardinal symptoms (i.e., Nausea and/or Vomiting, Sensitivity to light, and Sensitivity to sound) are not included in the 5 most common individual non-headache symptoms, cardinal symptoms will be summarized individually as well. If difficulty with concentration and/or thinking clearly is included in the 5 most common individual non-headache symptoms, monthly days with individual non-headache symptom will only be summarized in the other 4 most common individual non-headache symptoms.

For analysis purposes, four weeks (28 days) will be considered as one month. On a daily basis during the 28 days of eDiary baseline period and throughout the open-label treatment period, participants are to record eDiary information on the duration of headache, headache specific characteristics and symptoms, the pain intensity, use of any acute headache pain medication, and non-headache symptoms. Daily headache diary data consists of data from "Today's Diary" completed on that day, "24-Hour Recall of Yesterday's Diary" and "Yesterday's Additional Diary" completed on the following day. Participants are to report headache data in "Today's Diary" in the evening at any time from 19:00 to 23:59 and to complete "Yesterday's Additional Diary" on the following day to add the remaining headache data of previous evening until midnight. In case participants miss "Today's Diary," they can report the whole-day headache data in "24-Hour Recall of Yesterday's Diary" on the following day. In case participants miss "Yesterday's Additional Diary," headache data from "Today's Diary" alone will be used as daily headache diary data. If "Today's Diary," "24-Hour Recall of Yesterday's Diary" and "Yesterday's Additional Diary" are all missing on one day, the daily headache diary data will be treated as missing.

Daily headache diary data will be merged from "Today's Diary," "24-Hour Recall of Yesterday's Diary" and "Yesterday's Additional Diary" as following and will be used to derive migraine day and headache day.

- Daily headache total duration: summation of headache durations from "Today's Diary" and "Yesterday's Additional Diary"; or headache durations from "24-Hour Recall of Yesterday's Diary"

- Daily headache pain intensity: the worst pain intensity from "Today's Diary" "24-Hour Recall of Yesterday's Diary" and "Yesterday's Additional Diary"
- Daily headache characteristics and symptoms: present if present in one of "Today's Diary," "24-Hour Recall of Yesterday's Diary" and "Yesterday's Additional Diary"
- Daily acute headache medication usage: combination of acute headache medications usage from "Today's Diary" and "Yesterday's Additional Diary"; or acute headache medications usage from "24-Hour Recall of Yesterday's Diary"
- Daily non-headache symptoms: present if present in one of "Today's Diary" "24-Hour Recall of Yesterday's Diary" and "Yesterday's Additional Diary."

If a participant confirmed no headache in eDiary (Q1 in Today's Diary, Q2 in Yesterday's Additional Diary, or Q2 in 24-Hour Recall of Yesterday's Diary), then the participant will not answer subsequent questions related to headache symptoms, duration, and acute headache medication use by design. Thus, the acute medication use for that diary ('Today,' '24-Hours Recall,' or 'Yesterday's Additional') will be treated as 'No' when deriving acute medication use day. However, the participants will continue to answer subsequent questions related to non-headache symptoms.

The monthly migraine days is defined the total number of recorded migraine days in the eDiary divided by the total number of days with eDiary records during each monthly period and multiplied by 28. For baseline, a minimum of 20 days' eDiary data during the 28 days of eDiary baseline period is required for the migraine days to be evaluable. For each postbaseline 4-week treatment period, a minimum of 14 days' eDiary data during that period is required for the migraine days to be evaluable. If a participant does not have at least 14 days of diary data for a monthly treatment period, the migraine days for that period will be considered as missing. Migraine days will be derived for each participant at baseline and for each postbaseline monthly treatment period (Weeks 1-4, 5-8, 9-12, 13-16, 17-20, 21-24). The same method to derive monthly migraine days will be used to derive monthly headache days, monthly moderate or severe headache days, monthly cumulative hours of headache, monthly acute medication use days, monthly headache free days,

monthly complete migraine symptom-free day, monthly cardinal migraine symptom-free day, monthly day with an individual non-headache symptom.

If a participant confirmed that acute medications were taken and entered medications in the eDiary, then the acute medication use day will be set to 'Yes.' If a participant reports 'Yes' to the intake of allowed medication(s) to treat an acute migraine but does not list any of them in the diary, then the acute medication use days will not be counted in this situation and vice versa.

